- 1. The primary endpoint will be to prospectively investigate the efficacy of the nCAP Signal Relief Patch in reducing perioperative opioid requirement (up to 72 hours post-op) in opioid-naïve patients undergoing primary unilateral total hip or knee replacement surgery. Opioid requirement will be estimated following the placement of the patch.
- 2. The secondary endpoint will include the effects of nCAP Signal Relief Patch after the placement on postoperative pain, functional recovery, time to discharge from the hospital, and opioid related complications, such as, PONV, itching, sleep disorders, respiratory depression, and urinary retention.

Study Design

The proposed pilot study will be conducted as a single-center prospective, randomized, open label trial at the University of Pittsburgh Medical Center (UPMC) Shadyside Hospital.

Institutional review board approval will be obtained before eligible patients are recruited and consented. The trial will be registered at www.clinicaltrial.gov before beginning recruitment.

The efficacy of this device will be established by comparing postoperative opioid requirement to maintain pain scores \leq 4 using a Numerical Rating Scale (NRS). Accordingly, pain will be treated according to the following protocol: pain scores \leq 4, non-opioid analysics, pain scores between 4 and 6 oxycodone 5 mg q 4 hrs and \geq 7, oxycodone 10 mg, Hydromorphone IV 0.2-0.5 mg q 3 hr. Data collected following the placement in the treatment group (Standard of Care ERAS protocol + nCAP Signal Relief Patch) will be compared to the data obtained in the control group (Standard of Care ERAS protocol).

Recruitment

Potential subjects may be given a recruitment flyer (attached) in the office of surgeons Drs.

[name], [name], or [name]. The potential subjects who receive a flyer will then have the option of contacting the study team to discuss the study further, or, if they express interest in participating in the surgeon's office, their name will be given to the study team from the surgeon's office staff.

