After surgery, the subjects randomized to the intervention group will have the nCAP Signal Relief patch applied to their surgical dressing by a trained researcher in the immediate Post Anesthesia Care Unit (PACU). Subjects will be made aware at the time of consent and throughout the trial that they can drop out of the study at any time if they do not like wearing the nCAP Signal Relief Patch. The control group will not receive a patch but will receive the standard of care ERAS protocol. Subjects in the intervention group will be instructed to keep the nCAP Signal Relief Patch on their surgical dressing to avoid the risk for skin irritation.

Pain using a Numerical Rating Scale (NRS) at rest and with movement as well as opioid requirement will be assessed in the PACU and daily until discharge.

Subjects assigned to the intervention group should keep the nCAP Signal Relief Patch in place for 72 hours on their surgical dressing and they will be instructed to remove it at home.

Once the subject is discharged, they will be asked to complete a pain and opioid diary to record pain-related outcomes. They will be contacted via email (REDCAP survey) on post-operative day 1,2,3, 7, 14, and 30 to record postoperative opioid consumption, non-opioid consumption, NRS pain at rest and with movement, pain catastrophizing (via Pain Catastrophizing Scale) sleep quality (via PROMIS Sleep Disturbance Short Form 8a) and to assess functional recovery. Functional recovery will be assessed by determining the patient ability to walk 100 feet, go up 5 steps and raise their leg on postoperative days 1, 2, 3, 7, 14, and 30 as well as the pain associated with it. Patient satisfaction with pain management after surgery will be assessed at the 30 day follow up (0- least satisfied to 10-most satisfied). Subjects who are contacted via REDCap to complete follow-up questionnaires and do not complete them on the day they are assigned will be contacted via telephone for a reminder. They will be considered lost to follow up after 3 phone attempts.

Information will be collected from the medical record, including: patient demographics, medical history, medication summary while in the hospital, as well as progress notes from the entire encounter to determine the existence of adverse events.

Pre-and-Post Metric Evaluation

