The use of a non-pharmacological nCAP Signal Relief Patch has the possibility of providing analgesia to post-surgical patients and reducing the number of opioids required following surgery. This will significantly impact patient outcomes, as patients will experience fewer opioid-related side effects (such as respiratory depression, post-operative nausea and vomiting, constipation, and delirium). This will also impact clinicians caring for post-operative patients, as there is the real potential they will have fewer conditions to monitor and treat as the patient recovers from surgery. The projected number of patients served by this project will initially be 70 enrolled participants at Shadyside Hospital, however, the data collected from this trial will serve countless patients and the community at large as physicians strive to move away from opioid use following surgery. Data collected from this pilot study will support a future proposal to the National Institute of Drug Abuse (NIDA) to fund a full-scale, randomized, placebo-controlled trial using the nCAP Signal Relief Patch.

Perhaps most importantly, the investigative use of the non-invasive nCAP Signal Relief patch has the ability to significantly decrease opioid requirement, postoperative pain, the hospital length of stay, the needs for opioid prescription following discharge from the hospital, improve early functional recovery, and increase patient satisfaction.

Being able to offer the orthopedic patients at UPMC Shadyside Hospital such an alternative might represent a non-pharmacological approach to pain management and an alternative to opioid, increase patient satisfaction, and improve early functional recovery.

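### Four of the five named opioid-related complications have no stated source after discharge, so their observation window is length of stay, an outcome the patch is expected to shorten

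*Protocol*

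**What the plan says.** Protocol, Specific Aims, item 2, lists among the secondary endpoints "time to discharge from the hospital, and opioid related complications, such as, PONV, itching, sleep disorders, respiratory depression, and urinary retention". These are to be assessed after patch placement, with no stated end. The 72-hour limit in that section belongs to the primary opioid endpoint in item 1.

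Protocol, Data Collection and Outcome Measures, gives the sources:

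- **Adverse events:** the medical record, including "progress notes from the entire encounter to determine the existence of adverse events".
- **Follow-up surveys:** six e-mailed surveys between POD 1 and POD 30, whose purpose is given as "to record postoperative opioid consumption, non-opioid consumption, NRS pain at rest and with movement, pain catastrophizing". Sleep is among the other items, measured by the PROMIS Sleep Disturbance form, as is functional recovery. Satisfaction is added at day 30.
- **Diary:** after discharge, "they will be asked to complete a pain and opioid diary to record pain-related outcomes".
- **Patch wear:** the patch stays "in place for 72 hours on their surgical dressing and they will be instructed to remove it at home".

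Protocol, Pre-and-Post Metric Evaluation, says the patch "has the ability to significantly decrease opioid requirement, postoperative pain, the hospital length of stay".

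The SAP does not list complications among its measurements and sets no window for them. For categorical outcomes it plans chi-square or exact tests of proportions, with no adjustment for time observed.

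**The concern.** Two separate problems follow.

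**Incomplete capture.** The plan expects subjects to go home before the patch comes off, and it records opioid use at home. Nausea or vomiting, itching and urinary retention at home have no stated route into the data. This holds whether or not the arms differ in length of stay.

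**Unequal windows.** For these four complications a subject is observed only until discharge. Discharge time is a post-randomization outcome, a secondary endpoint in its own right, and in an open-label trial it can be moved by expectation. A plain comparison of proportions then sets the arms side by side over windows that treatment may have made unequal.

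The protocol says fewer opioid side effects are an expected benefit and that these data will support a proposal for a full-scale trial. A difference in complications that time under observation could explain would be weak support for it.

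**Working it through.** **Step 1: match each named complication to its stated sources.**

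| Complication | Hospital record | POD 1–30 surveys | Diary |
|---|---|---|---|
| PONV | yes | not named | not named |
| Itching | yes | not named | not named |
| Respiratory depression | yes | not named | not named |
| Urinary retention | yes | not named | not named |
| Sleep disorders | yes | PROMIS Sleep Disturbance 8a | not named |

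Four of the five have the hospital record as their only stated source. Sleep is also measured at baseline and on the same survey days in both arms.

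**Step 2: is there a plan figure to reproduce?** No. The documents give no length of stay, complication rate or event timing. Everything in steps 3 and 4 rests on assumed values and shows only how the size varies.

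**Step 3: size of the artefact when the patch has no effect on complications.** Assumptions: control risk over the stay p = 30%, control stay 36 h, patch stay 24 h, and the same hazard over time in both arms. Let f be the share of the 36-hour cumulative hazard that has accrued by 24 h. The patch arm then records 1 − (1 − p)^f = 1 − 0.7^f.

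- Constant hazard: f = 24/36.
- Hazard decaying with half-life h: f = (1 − 2^(−24/h)) / (1 − 2^(−36/h)).

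| Hazard | f | Patch arm records | Difference from 30% |
|---|---|---|---|
| Half-life 6 h | 0.9375/0.9844 = 0.952 | 28.8% | 1.2 points |
| Half-life 12 h | 0.75/0.875 = 0.857 | 26.3% | 3.7 points |
| Half-life 24 h | 0.5/0.6464 = 0.773 | 24.1% | 5.9 points |
| Constant | 24/36 = 0.667 | 21.2% | 8.8 points |

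Equal stays give f = 1 and a difference of zero.

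Varying the stay under a constant hazard, with control risk still 30%: a patch-arm stay shorter by 10%, 25% or 50% gives 0.7^0.9, 0.7^0.75 or 0.7^0.5 event-free. The recorded risks are 27.5%, 23.5% and 16.3%.

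**Step 4: set this against the noise.** The protocol's Treatment Groups section gives 30 per arm. For 30% versus 21.2%, the standard error of the difference is √(0.30×0.70/30 + 0.212×0.788/30) = √(0.00700 + 0.00557) = 0.112, or about 11 points. Even the constant-hazard artefact is below one standard error. The approximate chance that it reaches two-sided 0.05 (sidedness assumed) at 30% control risk is 8% for a stay 25% shorter and 24% for one 50% shorter. The main risk is a misleading estimate rather than a false significant result.

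**The case against.** The strongest reply is that this may amount to very little. The expected reduction in length of stay is a general statement of promise with no size attached. If the four complications occur mostly in the first hours after surgery, discharge cuts off few of them and the artefact is 1 or 2 points. The trial is a 60-subject pilot, this is one part of a multi-part secondary endpoint, and the primary endpoint is untouched. All of that stands, and it limits the weight of the point.

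The causal path also runs both ways. Vomiting, urinary retention or respiratory depression can keep a patient in hospital. If the patch truly reduced them, shorter stays would follow, and part of an observed difference would be a real effect. That stands too: earlier discharge in the patch arm would not by itself show that the comparison is biased.

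A reader might infer three stronger claims that the documents do not support:

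- That every opioid-related complication is captured only in hospital. Sleep is surveyed to POD 30.
- That the patch arm will show fewer complications through observation time alone. This needs unequal stays and events after the earlier discharge, and the documents quantify neither.
- That a stated 72-hour complication objective goes unanswered. The protocol attaches 72 hours only to the primary endpoint. For complications the defect is that no window is defined.

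None of this supplies a post-discharge source for the four complications or a common window for the two arms.

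**Conclusion.** The point holds in a limited form. As written, PONV, itching, respiratory depression and urinary retention are counted only up to discharge, events at home are missed in both arms, and the window varies with an outcome the patch is expected to change. The incomplete capture follows from the text alone.

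The between-arm bias is possible, not established. Under the assumptions in the working it ranges from about 1 to 9 points and favours the arm discharged earlier, whichever that is. Its true size cannot be obtained from the documents and could be near zero. This is a cheap improvement to a secondary endpoint, held with moderate confidence.

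**What to change.** 1. Add yes/no items for nausea or vomiting, itching and urinary retention to the REDCap surveys already sent on POD 1, 2 and 3. Ask the same items of subjects still in hospital on those days. Word each item to cover the time since the previous contact, so that the three answers span the whole window.
2. Define the endpoint as any such event from patch placement, or the matching PACU time in controls, to 72 hours in both arms. Starting at placement follows Specific Aims. Ending at 72 hours is a choice that aligns it with the primary endpoint's window.
3. Report chart-recorded events, including respiratory depression, separately, labelled as in-hospital only, with length of stay by arm beside them.
4. Put the endpoint, its window and its sources in the SAP.

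**Cost:** three survey items on existing contacts, the same questions put to inpatients, and a short amendment to the protocol and SAP. No visits are added.

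**Downsides:** surveys are slightly longer, recorded rates of mild events will rise, and some surveys will not be returned. Self-report in an open-label trial can also be shaped by expectation, so the change equalises the window but does not remove reporting bias. That is why the chart-based result should be shown alongside. Respiratory depression would still be observed only over the stay.

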Each subject will undergo surgery and anesthesia using the approved ERAS protocol.

Control Arm (n=30): Control group will receive approved ERAS multimodal anesthesia protocol (standard of care).

Interventional Arm (n=30): Intervention group will receive approved ERAS multimodal anesthesia protocol plus an nCAP Signal Relief Patch.

Data Collection and Outcome Measures

After signing an informed consent, subjects will complete the PROMIS Emotional Distress – Anxiety – Short Form 8a before completing any other questionnaires. Subjects who have a raw score <19 will be enrolled in the study. Any subject who scores \ge 19 will be considered a screen failure and excluded from the study.

Once the subject is enrolled, they will be asked to complete the Pain Catastrophizing Scale (PCS), the PROMIS® Emotional Distress-Depression - Short Form 8a, and the PROMIS® Item Bank v1.0 – Sleep- Disturbance – Short Form 8a prior to surgery. The subject will also conduct a baseline functionality test to assess mobility and strength in their leg. The functional recovery will be assessed by determining the patient ability to walk 100 feet, go up 5 steps and raise their leg on the day of surgery. Scores can be 0 (no ability to raise the leg), 1 (some ability to raise the leg), and 2 (complete ability to raise the leg).

Once these assessments are completed, subjects will be equally randomized to the intervention group (nCAP signal relief Patch + standard of care) or control group (standard of care). Both the control group and intervention group will receive approved ERAS multimodal standard of care. Only the interventional group will receive an nCAP Signal Relief Patch.

Randomization will occur by assigning the participant a subject ID number, and this ID number will correspond to a treatment allocation based on a pre-designed randomization schema.

Subjects will undergo surgery using the approved ERAS anesthetic and post-operative pain management protocols.

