Study Title: A Pilot Study Investigating the nCAP Signal Relief Patch in Subjects Undergoing Primary Hip or Knee Replacement Surgery – A Pilot Trial

Principal Investigator: [name], PhD, MBA

IRB: STUDY22010018 NCT: 05252858

Statistical Analysis Plan Approval Date: 02/01/2022

Power calculation is for an anticipated 60 subjects who underwent TKA. Data is to be analyzed using intend-to-treat analysis plan. Data collection in this study includes the following measurements:

- Total opioid consumption (OME mg),
- Pain at rest and during movement rated on a standard Numerical Rating Scale (NRS, 0 = no pain and 10 = the worst pain imaginable),
- Area under the curve (AUC) for pain scores collected on POD 1, 2, 3, 7, 14, and 30,
- Time to discharge from the recovery room,
- Time to discharge from the hospital, and
- Overall subject satisfaction at the time of hospital discharge

The number of subjects requesting a prescription refill during the first 30-days post-operative will be calculated using the Pennsylvania Data Management Program.

Student's t-test, non-parametric Kruskal-Wallis test, or Pearson's chi-square test were used to determine differences in the distribution of continuous outcomes, and the chi-square test or exact test was used for differences in proportions for categorical outcomes between the treatment and placebo arms. Data will be presented as mean \pm standard deviation (SD) with a standard alpha set at 0.05.

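### The Protocol sets arms totalling 60 but projects 70 enrolled, nothing links the two totals, and the SAP describes its 60 as knee patients only

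*Protocol*

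**What the plan says.** Two sections of the Protocol and one sentence of the SAP bear on the size of the trial.

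- **Protocol, Treatment Groups.** The control entry begins "Control Arm (n=30", and the other arm reads "Interventional Arm (n=30): Intervention group will receive approved ERAS multimodal anesthesia protocol plus an nCAP Signal Relief Patch". Together they make 60.
- **Protocol, Pre-and-Post Metric Evaluation.** The count of patients served, given as a projection, "will initially be 70 enrolled participants at Shadyside Hospital".
- **SAP, opening paragraph.** "Power calculation is for an anticipated 60 subjects who underwent TKA". The next sentence specifies an intention-to-treat analysis.

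The Protocol also shows what it means by enrolment. Under Data Collection and Outcome Measures, after consent and the anxiety form, "Subjects who have a raw score <19 will be enrolled in the study". Anyone at or above that cut-off "will be considered a screen failure and excluded from the study". Enrolled subjects then complete further questionnaires and a baseline function test, and are randomised equally after that.

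The Inclusion Criteria admit elective primary unilateral hip or knee replacement. Neither document gives a power, an effect size, an SD, a loss allowance, a replacement rule, an interim look or a rule for closing enrolment.

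**The concern.** The planned number of subjects should have one value, and a reader should be able to tell whether it counts people consented, enrolled, randomised or evaluable. Here a trial that closes at 60 and one that closes at 70 could both be described as having gone to plan. A later reader could not tell completion from early stopping or over-enrolment. The point carries some weight even in a pilot, because the SAP sets a formal alpha of 0.05 and the Protocol says the data will support a funding proposal for a full-scale trial.

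The SAP sentence adds a second ambiguity. If its 60 are all the subjects, it misdescribes the population. If they are knee patients only, the hip patients come on top and no overall total is defined.

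**Working it through.** **1. Reproduce the agreed figure.** Treatment Groups: 30 + 30 = 60, which matches the SAP's 60. There are therefore two totals in play, 60 and 70. The gap is 70 − 60 = 10, or 10/60 = 16.7% of the smaller figure. The power calculation behind the 60 cannot be reproduced, because none of its inputs except alpha is given.

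**2. Can screen failures explain the 10?** The Protocol's order is: consent, anxiety form, enrolment if below 19, remaining baseline assessments, equal randomisation, surgery, patch in recovery. Subjects at or above 19 leave before they are enrolled. A count of 70 enrolled has already excluded them, so they are not the 10.

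**3. Can later loss explain it?** If 60 is the number wanted after loss at rate d:

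- 60/(1 − d) = 70 gives d = 1 − 60/70 = 14.3%.
- 60 × (1 + d) = 70 gives d = 70/60 − 1 = 16.7%.

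Neither rate appears in the documents. By the first formula, rounding up, common round allowances miss 70: 10% gives 67, 15% gives 71 and 20% gives 75. A loss allowance is possible but unstated.

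**4. What each reading means for the analysis set.** Under intention to treat, everyone randomised counts. If all 70 enrolled are randomised equally, the arms are 70/2 = 35 each and the set is 70. If 10 are lost between enrolment and randomisation, the arms are 30 each and the set is 60. The text does not settle which is meant.

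**5. Illustrative effect on sensitivity.** Assumptions of this review, not of the plan: two-sided 0.05, 80% power, two-sample t-test.

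- Normal approximation: d = (1.960 + 0.842) × √(2/n). For n = 30 this is 2.802 × 0.258 = 0.72 SD. For n = 35 it is 2.802 × 0.239 = 0.67 SD.
- Noncentral t: 0.736 SD at n = 30 and 0.679 SD at n = 35.
- With an assumed true difference of 0.7 SD, t-test power is 76% at 60 and 82% at 70.

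**6. A hypothetical double test.** If the arms were compared at 60 and again at 70, each at |Z| > 1.96, the two statistics would have correlation √(60/70) = 0.926. The overall type I error, 1 − P(|Z₁| < 1.96 and |Z₂| < 1.96), is then 6.8%. Nothing in the documents plans such a comparison.

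**7. Population.** The Inclusion Criteria say hip or knee, while the SAP's power sentence says knee replacement. Because 60 equals the two Protocol arms combined, the likelier reading is that the SAP means the whole trial and names the wrong population. The SAP does not confirm that.

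**The case against.** The best defence is that the two operative statements agree. The arm sizes and the SAP both give 60, and the 70 appears only in a narrative about the project's impact, where it is called projected and qualified as initial. Extra recruitment to cover loss is ordinary practice. Intention to treat does not forbid recruiting more so that about 60 have outcome data, and it does not reach subjects who leave before randomisation. The Protocol allows withdrawal at any time and defines loss to follow-up. In a pilot, the difference between 0.74 and 0.68 SD is small.

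Most of this stands, and it limits the point to an unreconciled total. It does not remove the point: no sentence says that the 70 includes an allowance. If the loss falls after randomisation, 30 per arm is no longer the number allocated.

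A reader might infer three stronger things that the documents do not support:

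- **That 70 enrolled must mean 35 per arm.** Enrolment precedes the remaining baseline assessments and randomisation, so subjects can be lost in between.
- **That recruitment will be stopped according to the results.** The trial is open label, so allocation is known, but that is not the same as testing between arms during accrual. No interim look is planned, and the 6.8% shows only what an open target would leave possible.
- **That the trial was powered at 80% for 0.74 SD.** That figure is worked back from 60 with an assumed power. The plan states neither.

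**Conclusion.** The inconsistency is real and the text is wrong as written. The Protocol carries two totals, 60 and 70, ten subjects apart, with nothing to reconcile them, and the SAP attaches its 60 to a narrower population than the trial admits. Screen failure is ruled out as the explanation by the Protocol's own use of enrolled. A loss allowance of about 14% remains plausible but is nowhere stated.

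The consequence is moderate. The intention-to-treat set could be 60 or 70, with a detectable difference of 0.74 or 0.68 SD if 80% power and two-sided 0.05 are assumed. The finding is an unfixed target. It is not evidence of optional stopping, and it does not make the trial invalid. The correction should be made because it concerns a core design figure and is easily done.

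**What to change.** 1. State one number to be randomised, the same in the Protocol's Treatment Groups, its Pre-and-Post Metric Evaluation and the SAP's opening paragraph: either 60 (30 per arm) or 70 (35 per arm). The sponsor should choose.
2. Say what 70 counts (consented, enrolled or randomised), and give any loss allowance with its rate and the stage at which the loss is expected.
3. State that recruitment closes when the fixed number has been randomised, regardless of results.
4. Change the SAP's power sentence to refer to hip or knee replacement.
5. Give the sponsor's own power, sidedness, effect size and SD with that sentence. The 0.74 and 0.68 SD above are illustrations and should not be adopted as the plan's figures.

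The cost is wording in three places and no new procedure. If 60 is kept, no extra subjects are needed. If 70 randomised is intended, that is ten more than the arm sizes now show. Stating the power inputs may make the trial's sensitivity look less favourable than the bare sentence suggests.
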